### **3.7. Safety and other Analysis**

#### **3.7.1. Adverse Events**

Summaries will be presented by treatment group and overall.

Adverse events will be coded using the Medical Dictionary for Regulatory Activities (MedDRA) version 19.0. Treatment-emergent AEs (TEAEs) are defined as AEs that are newly occurring or worsening from the time of the first dose of study drug.

An overview table, including number of subjects with any TEAEs, serious adverse events (SAEs), study drug related TEAEs, TEAE by severity, and AE leading to discontinuation will be summarized.

In addition, the TEAEs will be summarized for the following:

- TEAEs by System Organ Class (SOC) and Preferred Term (PT)
- TEAEs by SOC, PT, and severity
- Drug Related TEAEs by System Organ Class and Preferred Term
- SAEs by System Organ Class and Preferred Term
- AEs leading to discontinuation by System Organ Class and Preferred Term

A subject having the same AE (as determined by the coded MedDRA preferred term) more than once will be counted only once in the number and percentage of subjects' calculation for that AE. Similarly, if a subject had more than one AE in a System Organ Class, the subject will be counted only once in the number of subjects with an AE for that System Organ Class. If a subject has the same AE on multiple occasions, the highest severity (severe > moderate > mild) recorded for the event will be presented in the AEs by severity table. Treatment-related AEs are defined as those events with a 'Relationship to Study Treatment' recorded on CRF as 'Definitely Related', 'Probably Related' or 'Possibly Related', others will be not related AEs.

Listings for all AEs, SAEs, and AEs leading to discontinuation will be presented.

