### **13.3. Relationship to Study Drug**

The assessment of study drug relationship to each AE will be reported on the appropriate source document (and SAE form, in the event of an SAE) by the investigator (or designated sub-investigator) according to his/her best clinical judgment. The criteria listed in [Table 7](#) should be used to guide this assessment. Please note that not all criteria must be present to be indicative of a particular drug relationship. All study drugs are considered “test drugs” for the purposes of the definitions listed in the table.

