**Table 7: Adverse Event Causality Guidelines**

Relationship	Criteria for assessment
Definitely related	
There is evidence of exposure to the test drug. AND The temporal sequence of the AE onset relative to administration of the test drug is reasonable. The AE is more likely explained by the test drug than by another cause. Dechallenge (if performed) is positive. Rechallenge (if feasible) is positive. The AE shows a pattern consistent with previous knowledge of the test drug or test drug class.

Probably related	
There is evidence of exposure to the test drug. AND The temporal sequence of the AE onset relative to administration of the test drug is reasonable. The AE is more likely explained by the test drug than by another cause. Dechallenge (if performed) is positive.

Possibly related	
There is evidence of exposure to the test drug. AND The temporal sequence of the AE onset relative to administration of the test drug is reasonable. The AE could have been due to another equally likely cause. Dechallenge (if performed) is positive.

Probably not related	
There is evidence of exposure to the test drug. AND There is another more likely cause of the AE. Dechallenge (if performed) is negative or ambiguous. Rechallenge (if performed) is negative or ambiguous.

Definitely not related	
The subject did not receive the test drug. OR Temporal sequence of the AE onset relative to administration of the test drug is not reasonable. OR There is another obvious cause of the AE.

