### 13.4. Monitoring and Recording of Adverse Events

AE data collection will begin after a subject signs the ICF and will continue until completion of the End of Treatment/Early Termination visit (Day 169). Any AE or SAE having an onset after the End of Treatment/Early Termination visit will not be collected or reported unless the investigator feels that the event may be related to the study drug.

Subjects will be instructed by the investigator or designee to report the occurrence of any AE. All volunteered, elicited, and observed AEs are to be recorded on the AE eCRFs.

The investigator will assess all AEs regarding any causal relationship to the study drug (see [Section 13.3](#)), the intensity (severity) of the event, action taken, and subject outcome.

The following criteria should be used to guide the assessment of intensity (severity):

- **Mild:** Causes awareness of sign or symptom, but is easily tolerated; does not interfere with usual activities
- **Moderate:** Causes discomfort enough to interfere with usual activities
- **Severe:** Is incapacitating; results in inability to work or perform usual activities

[figure not shown]
All AEs will be followed until resolution, until deemed stable by the investigator, or until the subject is deemed by the investigator to be lost to follow-up.

For clinical study safety reporting purposes, the most recent version of the Investigator's Brochure will be used as the reference document to designate event expectedness.

Withdrawal from the study as a result of an AE and any therapeutic measures that are taken shall be at the discretion of the investigator. If a subject withdraws from the study for any reason, any ongoing AEs will be followed until resolution, until deemed stable by the investigator, or until the subject is deemed by the investigator to be lost to follow-up.

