### 13.5. Reporting of Serious Adverse Events

All SAEs must be reported to Alkermes, via  within 1 business day of discovery, by faxing the report to the following:

Attention:  Drug Safety  
PHONE Number:   
FAX Number:   
FAX Number:   

The written report should be submitted on the SAE form provided for this purpose. The report must include the investigator's opinion as to whether the event is study drug-related. If this relationship is determined to be possibly, probably, or definitely related to study drug, evidence to support this assessment must also be provided.

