## **6.2. Safety Data Handling**

All efforts should be made to obtain the missing information from the investigator.

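### SAP 3.7.1 defines not-related AEs by a catch-all, so a causality rating still missing after query would, read literally, be counted as not related

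*SAP*

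**What the plan says.** SAP section 3.7.1 sorts adverse events by the relationship "recorded on CRF as 'Definitely Related', 'Probably Related' or 'Possibly Related', others will be not related AEs". The closing words, "others will be not related AEs", are the catch-all at issue. The result feeds two outputs in that section: the drug-related row of the overview table, and the table headed "Drug Related TEAEs by System Organ Class and Preferred Term". Both are presented by treatment group and overall.

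The causality scale is in Protocol Table 7. It has five levels. Three are the ratings named in the SAP; the other two are "Probably not related" and its definite counterpart. There is no level for an unknown or unassessed relationship.

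The protocol expects every event to be rated. Section 13.4 states: "The investigator will assess all AEs regarding any causal relationship to the study drug". Section 13.3 says where the rating goes: "The assessment of study drug relationship to each AE will be reported on the appropriate source document", and on the SAE form if the event is serious. Section 13.5 adds for SAEs: "The report must include the investigator's opinion as to whether the event is study drug-related".

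On missing safety data, SAP section 6.2 has one sentence: "All efforts should be made to obtain the missing information from the investigator". It does not say what to do if the information cannot be obtained.

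**The concern.** A blank field is not one of the three ratings that the SAP counts as related. The next clause assigns whatever is left to the not-related side. A programmer who codes the sentence as written would put an unrated event there, and nothing in section 6.2 would stop it. The classification would then come from the wording of a residual clause and not from anyone's judgement of the event, and it would fall in the favourable direction.

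Safety and tolerability are part of the primary objective, and the drug-related TEAE table is one of the main displays for it. A safety summary should not turn an absent rating into a statement that the drug was not the cause. A sentence in the SAP can prevent that.

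**Working it through.** The documents give no figure to reproduce: no expected AE rate, no expected rate of missing ratings and no sample size calculation. The check has two parts, a reading of the rule and a count of what it could change.

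**Where each CRF entry goes under the SAP sentence**

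| CRF entry | On the Protocol Table 7 scale? | SAP 3.7.1 class |
|---|---|---|
| Definitely, probably or possibly related | Yes | Related |
| Probably not or definitely not related | Yes | Not related, correctly |
| Blank after query | No | Not related, through the catch-all only |

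Only the last line is in question. Compared with counting a blank as related, the literal rule gives a drug-related count that is equal or lower, never higher.

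**Size per subject**

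Input: N = 50, the approximate enrolment in the Protocol synopsis and section 7.1, assuming all are dosed and so enter the safety population. Let *m* be the number of subjects whose only candidate for the drug-related row is a TEAE with a blank rating. The SAP counts each subject once per row, so a subject who already has a related-rated TEAE in that row does not add to *m*.

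Gap = 100 × m / N percentage points, so one subject is 100 × 1 / 50 = 2 points. As an illustration, assume 15 of 50 subjects have a TEAE rated related (15/50 = 30%):

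| m | Literal rule | Missing counted as related | Gap (points) |
|---|---|---|---|
| 0 | 15/50 = 30% | 15/50 = 30% | 0 |
| 1 | 30% | 16/50 = 32% | 2 |
| 2 | 30% | 17/50 = 34% | 4 |
| 3 | 30% | 18/50 = 36% | 6 |
| 5 | 30% | 20/50 = 40% | 10 |

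The gap is the same if the assumed starting figure is 10/50 or 20/50.

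The tables are also split into the three switch-reason groups of SAP 3.1. Their sizes are not given. If they were equal, each would hold 50/3 ≈ 17 subjects, and one subject would be 100/17 ≈ 6 points within a group.

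**Whether any blank would occur**

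This needs two inputs that the documents do not give: the number of AEs, *A*, and the share still unrated after query, *b*. If blanks occur independently, the chance of at least one is 1 − (1 − b)^A and the expected number is A × b. With an assumed A = 150:

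| b | Chance of at least one blank | Expected blanks |
|---|---|---|
| 0% | 0% | 0 |
| 0.2% | 26% | 0.3 |
| 0.5% | 53% | 0.75 |
| 1% | 78% | 1.5 |
| 2% | 95% | 3 |

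With A = 100 the chance at b = 0.5% is 39%; with A = 200 it is 63%. So one or a few blanks are possible even with good query resolution, and none at all is also possible. These are blank AEs, not affected subjects. *m* can be smaller, because a blank matters to a row only if the subject has no related-rated TEAE in it.

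**The case against.** The strongest reply is that the sentence was never about missing data. It speaks of ratings recorded on the CRF and names three of the five levels, so the natural meaning of the remainder is the other two levels, and for those the rule is right. The SAP nowhere mentions a missing rating.

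Blanks should also be uncommon by design. A rating is required for every AE and in every SAE report. Monitors compare source records with the eCRF (Protocol 16.1), data entries are verified (Protocol 18.1), and SAP 6.2 has missing items pursued with the investigator. The consequence is limited as well: the study is open-label with no comparator, the AE summaries are descriptive, and every AE is listed.

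All of this stands as a limit on likelihood and size. It does not remove the point. If the remainder means only two named ratings, the SAP can name them. If a blank does survive the queries, the written sentence decides its class and no other text in either document overrides it. Counting a blank as related is itself a convention, and it can err upward. For a safety summary that is the more protective direction.

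**Conclusion.** The point holds as a minor one. SAP 3.7.1 has no explicit rule for a causality rating that stays missing, its catch-all would by default class such an event as not related, and SAP 6.2 supplies no fallback. The drug-related TEAE counts could be understated by at most 2 percentage points per affected subject in the overall column, assuming 50 dosed subjects, and by nothing if no rating is blank at lock. For a real understatement, three things must be true: a rating is still blank after query, the event was in fact drug-related, and the subject has no other related-rated TEAE in the same row.

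A reader might infer three stronger things that the documents do not support:

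- **That the SAP does understate drug-related events.** It shows only that it could. No rate of missing ratings is given, and the protocol requires a rating for every AE.
- **That blanks would cluster in subjects who are lost or withdrawn.** Causality is the investigator's own judgement (Protocol 13.3) and the missing item is sought from the investigator, so the subject's absence need not leave it blank. Neither document says otherwise.
- **That partly dated AEs are resolved in the favourable direction in the same way.** SAP 6.3 covers medication dates only, and no stated rule sends an AE with a partial onset date to the non-treatment-emergent side. Silence has no direction, so this does not belong to the present point.

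**What to change.** In SAP 3.7.1, replace the catch-all with wording such as:

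> *AEs rated Probably not related or Definitely not related are classed as not related. A TEAE whose relationship is still missing after query is counted as related in the summary tables, and its relationship is shown as missing in the listings.*

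A cross-reference from SAP 6.2 would make clear what happens once queries are exhausted.

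The cost is a short wording change, with no new data collection and no effect on total TEAE, SAE or discontinuation counts. The drug-related count may become slightly less favourable. If every AE is rated at lock, the tables are unchanged.

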### 3.7.2. Prior and Concomitant Medications

Prior medications are defined as medications that started and stopped prior to the first dose of study drug. Concomitant medications are defined as medications that started after or were ongoing at the time of the first dose of study drug. All medications will be coded using the World Health Organization Anatomical Therapeutic Chemical (WHO-ATC) Drug dictionary version March 2016 of medical codes (WHO Drug). All prior and concomitant medications will be summarized and listed.

### 3.7.3. Clinical Laboratory Parameters

Laboratory parameters will be presented in conventional (CN) units. Only scheduled lab parameters will be included in the laboratory results summaries.

Observed values and change from baseline will be summarized by treatment group and overall at each visit for chemistry and hematology parameters. Additionally, the number and percentage of subjects with potentially clinically significant (PCS) results will be presented (and by sex for prolactin). Only subjects with non-PCS values at baseline and PCS at any post-baseline visit will be included in the summary table. All PCS values (including baseline) will be included in supportive listings. For urinalysis, rate of abnormalities will be summarized.

Criteria for PCS are listed in [Table 2](#):

**Table 2: Clinical Laboratory Parameters - PCS Criteria**

Lab Parameters	Criteria (Conventional units)
Chemistry	
Albumin	< 2.5 g/dL
Alkaline phosphatase(ALK-P)	≥ 3 x ULN
Alanine aminotransferase	≥ 3 x ULN

Lab Parameters	Criteria (Conventional units)
ALT	
Aspartate aminotransferase AST	$\geq 3 \times \text{ULN}$
Bilirubin, Total	$\geq 2.0 \text{ mg/dL}$
Blood Urea Nitrogen (BUN)	$> 30\text{mg/dL}$
Creatinine Kinase (CK)	$> 3 \times \text{ULN}$
Creatinine	$\geq 2.0 \text{ mg/dL}$
Creatine phosphokinase (CPK), Total	$\geq 3 \times \text{ULN}$
Cholesterol, Total, fasting	$\geq 240 \text{ mg/dL}$
Cholesterol, HDL, fasting	$\leq 30 \text{ mg/dL}$
Cholesterol, LDL, fasting	$\geq 160 \text{ mg/dL}$
Glucose	$< 50\text{mg/dL}$ or $\geq 200 \text{ mg/dL}$
Lactic Dehydrogenase (LDH)	$> 3 \times \text{ULN}$
Potassium	$< 3 \text{ mEq/L}$ or $> 5.5 \text{ mEq/L}$
Prolactin by gender	$> 1 \times \text{ULN}$ $> 2 \times \text{ULN}$ $> 3 \times \text{ULN}$
Sodium	$< 130 \text{ mEq/L}$ or $> 150 \text{ mEq/L}$
Triglycerides, fasting	Female $\geq 120 \text{ mg/dL}$ Male $\geq 160 \text{ mg/dL}$
Hematology	
Eosinophils	$> 1 \times 10^3 /\mu\text{L}$
Hematocrit	Female $\leq 32\%$ and 3 point decrease from baseline Male $\leq 37\%$ and 3 point decrease from baseline
WBC	$\leq 2.8 \times 10^3 /\mu\text{L}$ or $\geq 16.0 \times 10^3 /\mu\text{L}$
Neutrophils, absolute	$< 1.5 \times 10^3 /\mu\text{L}$
Platelet count	$< 75,100 \text{ cells}/\mu\text{L}$ or $\geq 700,000 \text{ cells}/\mu\text{L}$

### 3.7.4. Vital Signs

Observed values and changes from baseline values will be summarized by treatment group and overall and assessment time point for each vital sign parameter. Additionally, the number and percentage of subjects with potentially clinically significant (PCS) results will be presented.

Criteria for PCS are listed in [Table 3](#).

**Table 3: Vital Signs - Clinical Laboratory Parameters - PCS Criteria**

Parameter	PCS Criteria
Supine Systolic blood pressure	Low: $\leq 90$ mm Hg and decrease $\geq 20$ mm Hg
	High: $\geq 180$ mm Hg and increase $\geq 20$ mm Hg
Supine Diastolic blood pressure	Low: $\leq 50$ mm Hg and decrease $\geq 15$ mm Hg
	High: $\geq 105$ mm Hg and increase $\geq 15$ mm Hg
Supine Pulse	Low: $\leq 50$ bpm and decrease $\geq 15$ bpm
	High: $\geq 120$ bpm and increase $\geq 15$ bpm

**3.7.5. Body Weight, Waist Circumferences, and Body Mass Index (BMI)**

Body weight (kg) and waist circumferences (baseline and change from baseline) will be summarized by treatment group and overall. The number and percentage of subjects with PCS values ( $\geq 7\%$  increase or  $\geq 7\%$  decrease at any post-baseline visit will be summarized by treatment group and overall. The PCS increase in weight will also be summarized by baseline BMI category (Underweight [ $<18.5$  kg/m^2], Normal [ $\geq 18.5$  to  $<25$  kg/m^2], Overweight [ $\geq 25$  to  $<30$  kg/m^2], and Obese [ $\geq 30$  kg/m^2]).

**3.7.6. Injection Site Reactions**

All injection site reactions will be reported as AEs. Injection site reaction AE preferred terms (injection site pain, injection site erythema, injection site swelling, etc.) will be summarized by treatment group and overall.

**3.7.7. Columbia Suicide Severity Rating Scale (C-SSRS)**

The number and percentage of subjects with suicidal ideation and/or behavior (overall and for each subcategory) as assessed by the C-SSRS scale during the overall treatment period will be summarized by treatment group and overall using descriptive statistics.

**3.7.8. Extrapyrarnidal Symptom Rating Scale – Abbreviated (ESRS-A)**

Each subcategory (Parkinsonism, Dystonia, Dyskinesia, Akathisia), and total score of the Abbreviated Extrapyrarnidal Symptom Rating Scale (ESRS-A) will be summarized by treatment group and overall using descriptive statistics.

**3.7.9. Modified Medication Satisfaction Questionnaire (Modified –MSQ)**

The proportion of subjects for each category for each question at each visit will be summarized by treatment group and overall .

**3.7.10. Sexual Functioning Subscale from UKU Side Effect Rating Scale and CSFQ-14**

Observed values and changes of each CSFQ subscale and total score from baseline values will be summarized by gender and overall using descriptive statistics.

The proportion of subjects with each UKU side effect will be summarized by treatment group and overall using descriptive statistics.

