**Table 1: Schedule of Visits and Assessments**

	Screening	Treatment Period 						
		Day 1	Month 1	Month 2	Month 3 	Month 4	Month 5	Month 6 EOT/ET
		V1	V2	V3	V4	V5	V6	V7
Visit windows (days)		Day 1	22-36	37-64	65-92	93-120	121-148	149-183
4 week dosing target day		1	29	57	85	113	141	169
6 week dosing target day		1	May skip Visit 	43	85	May skip Visit 	127	169
Study Drug Administration		Injections are to be given monthly (6 total injections) or every 6 weeks (4 total injections) based on the dosing regimen selected; After Day 1, subsequent injections will occur 28 or 42 days following the previous injection						
Informed Consent	X							
Eligibility Criteria Review 	X	X						
Oral Aripiprazole Test Dose Administration 	X							
Drug Screen 	X							
12-Lead ECG	X							
Demographics and Medical History	X							
Reason for switching paliperidone/risperidone	X							
MINI (Modules I & J)	X							X
Height	X							
Pregnancy Testing 	X	X						

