## **11. QUALITY OF LIFE, DAILY AND SOCIAL FUNCTIONING**

The following assessments will be collected to characterize any change in quality of life, including daily and social functioning, after treatment with aripiprazole lauroxil:

- Heinrichs-Carpenter Quality of Life Scale (QLS)
- Negative Symptom Assessment-16 (NSA-16)
- Sexual functioning subscale from UKU Side Effect Rating Scale and CSFQ scores
- Personal and Social Performance scale (PSP)
- Total and individual items scores of the Modified MSQ

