## 12. OTHER ASSESSMENTS

The following assessments will be collected to explore potential changes in healthcare burden, cognition, insight, and psychosocial care needs following a transition to aripiprazole lauroxil:

- Health economics
  - Total healthcare costs as measured by TSR-6-Modified for Mental Health
- Functional Assessment
  - BIS
- Family Measures
  - CarerQOL-7D and VAS
  - Burden Assessment Scale
- Investigator- and Caregiver-Rated Cognition
  - Respective NY-AACENT subscales
- Substance Use
  - M.I.N.I. Module I (alcohol use disorder)
  - M.I.N.I. Module J (substance use disorder)

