## **3. DATA ANALYSIS**

### **3.1. General Statistical Methodology**

Descriptive statistics for continuous variables include n, mean, standard deviation, median, minimum, and maximum. Descriptive statistics for categorical variables include subject counts and percentages. All data summarized will have a corresponding listing created as well. All data listings, summaries, and statistical analyses will be generated using SAS® version 9.3 or higher.

Baseline is defined as the last non-missing value before study drug administration.

Study days will be numbered relative to the first day of study drug administration. The start of treatment (Day 1) is defined as the date on which a patient takes study drug. Days will be numbered relative to study start (i.e., ..., -2, -1, 1, 2, ...; with day 1 being the start of study drug and day -1 being the day before the start of study drug).

By visit summarization will be tabulated nominally at the visit information was collected. Treatment groups will be categorized into the following 3 groups based on the primary switch reasons:

1. Due to tolerability or metabolic effect
2. Due to suboptimal efficacy in negative symptoms
3. Due to suboptimal efficacy in positive symptoms

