### **3.7.13. Mini International Neuropsychiatric Interview (M.I.N.I.) Module I & J**

The proportion of subjects with Mini International Neuropsychiatric Interview (M.I.N.I.) Module I (alcohol use disorder) and Module J (substance use disorder) will be summarized by treatment group and overall.

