## **6.1. Analysis Visit Windows**

For all analyses for this study, the scheduled visit and/or time point from the CRF (ie, CRF visit) will be used as the analysis visit and/or time point. There would be one valid value of assessment kept for each scheduled analysis visit in summary/analysis statistics.

Unless specified otherwise, measurements collected from unscheduled visits, will not be included in the summary tables, except for PCS analysis, and will be included in the subject listings.

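### SAP 3.7.10 plans only the proportion of subjects with each UKU side effect, which cannot show how many effects resolved and how many appeared after the switch

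*SAP*

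**What the plan says.** Protocol Table 1 schedules the modified UKU at Screening, Day 1 and Month 6 EOT/ET. Protocol Section 11 places the UKU subscale in a list introduced with these words: "The following assessments will be collected to characterize any change in quality of life, including daily and social functioning, after treatment with aripiprazole lauroxil". Under Protocol 7.3.14.1 each item is scored 0 (none or doubtful), 1 (mild), 2 (moderate) or 3 (severe).

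The whole UKU analysis in SAP 3.7.10 is one sentence: "The proportion of subjects with each UKU side effect will be summarized by treatment group and overall using descriptive statistics". It names no visit, change from baseline, shift table or score that counts as having the effect. The treatment groups are the three switch-reason groups of SAP 3.1.

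Two general rules bear on the visit. SAP 3.1 states: "By visit summarization will be tabulated nominally at the visit information was collected". SAP 6.1 states, for all analyses, that "the scheduled visit and/or time point from the CRF (ie, CRF visit) will be used as the analysis visit and/or time point", and keeps one valid value per scheduled visit. SAP 3.1 also defines baseline for the whole study as the last non-missing value before study drug.

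The M.I.N.I. modules are treated in a similar way. SAP 3.7.13 reads: "The proportion of subjects with Mini International Neuropsychiatric Interview (M.I.N.I.) Module I (alcohol use disorder) and Module J (substance use disorder) will be summarized". Here too the breakdown is by switch-reason group, plus all subjects together. They are collected at Screening and Month 6.

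**The concern.** The study has no control arm, so its most direct evidence on the switch is what happens within each subject. For a side-effect scale that raises two questions: which symptoms present on the earlier injectable went away, and which were absent and then appeared. Tolerability or metabolic effect is one of the three switch reasons that define the analysis groups. Protocol Section 4 also calls it clinically important to compare the safety and tolerability profiles of the respective treatments.

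The UKU data can answer both questions, because each subject seen at EOT/ET should have ratings before and after the switch. The planned summary does not use that pairing. An unchanged proportion could mean that nobody changed, or that many improved while as many got worse.

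**Working it through.** The plan states no UKU rate, so there is no figure to reproduce. The check has a textual part and an arithmetic part. All counts in the arithmetic are assumptions, apart from the planned enrolment of about 50.

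**1. Comparison with neighbouring instruments**

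| Instrument | Rated (Protocol Table 1) | SAP analysis |
|---|---|---|
| UKU | Screening, Day 1, Month 6 | Proportion with each effect (3.7.10) |
| CSFQ-14 | Screening, Day 1, Month 6 | Observed values and change from baseline (3.7.10) |
| Modified MSQ | Screening (item 1), Month 6 | Category proportions at each visit (3.7.9) |
| Burden Assessment Scale, Birchwood Insight Scale | Screening, Month 6 | Observed values and change from baseline (3.7.11, 3.7.12) |

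The UKU shares a schedule and a SAP section with the CSFQ-14 but has no change analysis.

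**2. What the general rules supply**

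- Visit: SAP 3.1 and 6.1 probably supply it, by CRF visit.
- Baseline value: SAP 3.1 supplies it. This is Day 1 if the rating precedes the injection, which Table 1 does not state for the UKU.
- Within-subject comparison: no rule supplies it.
- Score that counts as present: no rule supplies it.

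**3. What two marginal proportions identify, with complete data**

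Among subjects with both ratings, let a = persisting, b = resolved, c = newly present and d = absent at both. A by-visit table gives a + b (baseline) and a + c (Month 6). Their difference gives b − c, but not b or c.

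Assume N = 50, with 20 affected before (40%) and 10 after (20%). Then b − c = 10. Since b cannot exceed 20, c can lie anywhere from 0 to 10:

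| Resolved b | New c | Persisting a = 20 − b | Absent d = 30 − c | Exact McNemar p |
|---|---|---|---|---|
| 10 | 0 | 10 | 30 | 0.002 |
| 15 | 5 | 5 | 25 | 0.041 |
| 20 | 10 | 0 | 20 | 0.099 |

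Here p = 2 × P(X ≤ c) with X binomial(b + c, 0.5). No UKU test is planned and none is proposed. The p-values only show how differently the same two percentages can read. With 15/50 before and 10/50 after (30% and 20%), b − c = 5, c again runs from 0 to 10, and p from 0.063 to 0.42.

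**4. With withdrawals**

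Protocol 6.4 does not replace withdrawn subjects, so denominators can differ between visits. Assume 20/50 at baseline and 16/40 at Month 6, both 40%. Let r be the number affected at baseline among the 40 with both ratings. Ten subjects are lost, so r lies between 20 − 10 = 10 and 20.

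- Smallest c: max(0, 16 − r), which is 0 when r is 16 or more.
- Largest c: 16. This needs 40 − r ≥ 16, so r ≤ 24, which always holds.
- Resolved b = r − a runs from 0 (r = 10, a = 10, c = 6) to 20 (r = 20, a = 0, c = 16).

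Two equal percentages therefore fit anything from 0/40 to 16/40 newly affected (0% to 40%).

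**The case against.** The strongest reply is that the plan does what the protocol promised. Protocol 14.6 says only that these data will be summarized, and 14.2 sets counts and percentages for categorical variables. The shift tables in Protocol 14.5 are for selected parameters, and the UKU is not named. The CSFQ-14 yields numeric scores, so its change from baseline does not oblige the UKU to have a shift table. Subject listings are planned, so with about 50 subjects the pairs can be recovered by hand. Mock tables sit in a separate document that is not available here. The UKU is listed under quality of life, not safety. Tolerability is also covered by treatment-emergent adverse events, prolactin by sex, CSFQ-14 change and the MSQ item comparing side effects with the previous injectable.

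Most of this stands, and it limits severity: there is no breach, and the UKU is one source among several. It does not remove the gap, because listings leave the derivation to the reader and Section 11 gives change as the purpose.

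A reader might infer something stronger, namely that symptoms on the earlier injectable and symptoms after the switch are merged in one proportion. The documents do not support that. SAP 6.1 covers all analyses and keeps one value per scheduled visit, and nothing says UKU visits are pooled. Other sections do use period-wide proportions (C-SSRS over the treatment period, weight change at any post-baseline visit), and 3.7.10 omits the each-visit wording of 3.7.9. That is a reason to name the visits, not evidence of pooling.

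**Conclusion.** The point holds for the UKU. It is collected before and after the switch to characterize change, and the SAP plans no within-subject analysis of it. By-visit proportions, the probable output, leave the numbers resolved and newly affected unidentified, and the score that counts as present is undefined. The non-identifiability is arithmetic and does not depend on the example. The widths shown (0 to 10 of 50, or 0 to 16 of 40) do depend on assumed prevalences and, in the second case, on an assumed loss of 10 subjects. They are not estimates for this trial.

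Severity is low to moderate: the outcome is descriptive and non-primary, and no decision rule depends on it.

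A reader might extend the same argument to the M.I.N.I. modules. It does not carry over: alcohol and substance use disorders are not symptoms of the earlier injectable. Exclusion criterion 5 also removes moderate to severe substance use disorder within the 12 months before screening, so a cross-table may be sparse.

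**What to change.** In SAP 3.7.10:

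- State that each UKU item is tabulated by visit (Screening, Day 1, Month 6 EOT/ET), with the number rated as denominator.
- Define an effect as present at a score of 1 or more.
- Add a shift table per item from baseline (last pre-dose value, normally Day 1) to EOT/ET, among subjects with both ratings. Give counts newly present (0 to 1 or more), resolved (1 or more to 0), persisting and absent, by switch-reason group and overall.

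In SAP 3.7.13, a Screening-by-Month 6 cross-table for each M.I.N.I. module is an optional, low-priority addition.

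The cost is one added table, or two with the M.I.N.I., from data already collected. There are no new visits and no added subject burden. Label: free improvement.
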